## **Data Management:**

Data will be stored in a HIPPA-compliant manner in a REDCap database accessible to only the PI and key study personnel at each participating center, and site coordinating center monitoring team (Vanderbilt University Medical Center). Uploaded files and patient data will be identifiable in raw form but de-identified chart and subject ID in REDCap with access restricted to implant sites and coordinating center.

## **Safety Reporting:**

Adverse events (AE) related to the drug or the procedure during the course of the study will be reported in the patient's record, and the investigator will give his or her opinion as to the relationship of the adverse event to study drug treatment.(i.e., the relationship will be reported as "related" or "unrelated" to the study drug administration).. If the adverse event is serious, it will be reported to Boehringer Ingelheim Pharmaceuticals, Inc. (BI), and IRB by the coordinating center and trial PI. All serious adverse events will be followed until resolution or stabilization. Results of the follow-up will be reported to BI and the IRB.

### Definitions of Adverse Events:

"An adverse event (AE) is defined as any untoward medical occurrence in a patient or clinical investigation subject administered a medicinal product and which does not necessarily have to have a causal relationship with this treatment.

An AE can therefore be any unfavourable and unintended sign (including an abnormal laboratory finding), symptom, or disease temporally associated with the use of a medicinal product, whether or not considered related to the medicinal product"

An AE or suspected adverse reaction is considered "serious" if, in the view of either the investigator or sponsor, it results in any of the following outcomes: death, a life-threatening adverse event, inpatient hospitalization or prolongation of existing hospitalization, a persistent or significant incapacity or substantial disruption of the ability to conduct normal life functions, or a congenital anomaly/birth defect. Important medical events that may not result in death, be life-threatening, or require hospitalization may be considered serious when, based upon appropriate medical judgment, they may jeopardize the patient or subject and may require medical or surgical intervention to prevent one of the outcomes listed in this definition. Examples of such medical events include allergic bronchospasm requiring intensive treatment in an emergency room or at home, blood dyscrasias or convulsions that do not result in inpatient hospitalization, or the development of drug dependency or drug abuse.

Acute minor or major complications following the implant procedure will be reported. Intra-operative major bleeding or device related (embolization, stroke, hemorrhage, etc.), will be reported as a procedural complication which is not study drug related. After the AM dosing of dabigatran post-operative day #1, and up to 90 days post procedure, AE's potentially related to study drug will need to be reported. Adverse events include events such as those described above that occur at any time from informed consent until 90 days post implant of the LAA closure Watchman device.

### Recording of Adverse Events:

All AEs will be documented. A description of the event, including its date of onset and resolution, whether it constitutes a serious adverse event (SAE) or not, any action taken (e.g., changes to administration), and outcome, will be provided, along with the investigator's assessment of causality (i.e., the relationship to the study treatment[s]) and determination of severity (e.g., mild, moderate, severe). For an AE to be a suspected treatment-related event, there should be at least a reasonable possibility of a causal relationship between the protocol treatment and the AE.

## **Bleeding events**

Patients will be carefully assessed for signs and symptoms of bleeding at each visit. Bleeding will be classified as major or minor using the following guidelines. Major bleeds will be further sub classified as either life-threatening or other major bleeds.

Major Bleeds:

Bleeding associated with a transfusion of at least 2 units of blood or packed cells.

Symptomatic bleeding in a critical area or organ requiring surgical or non-operative intervention: Intraocular, intracranial, intraspinal or intramuscular with compartment syndrome, retroperitoneal bleeding, intra-articular bleeding or pericardial bleeding.

Minor Bleeds:

Minor bleeds are clinical bleeds that do not fulfill the criteria for major bleeds. Minor bleeds are classified as associated with study medication discontinuation (temporary or permanent) or not.

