#### **Exclusion Criteria:**

1. Unable to give informed consent
2. History of confirmed allergy to dabigatran etexilate
3. Active cerebral bleeding, or active non-cerebral bleeding requiring blood transfusions (any absolute contra-indications to anti-coagulation).
4. History of intraocular, spinal, retroperitoneal or a traumatic intra-articular bleeding unless the causative factor has been permanently eliminated or repaired (e.g. by surgery)
5. Gastrointestinal (GI) haemorrhage within one month prior to screening, unless, in the opinion of the Investigator, the cause has been permanently eliminated (e.g. by surgery)
6. Major bleeding episode (reduction in the haemoglobin level of at least 2g/dL, transfusion of at least two units of blood, or symptomatic bleeding in a critical area

or organ) including life-threatening bleeding episode (symptomatic intracranial bleeding, bleeding with a decrease in the haemoglobin level of at least 5g/dL or bleeding requiring transfusion of at least 4 units of blood or inotropic agents or necessitating surgery) in one month prior to screening visit

7. Intolerance to dabigatran, if medication naïve, or other contra-indications as per the USPI, including ESRD on hemodialysis or GFR < 15ml/min, or concomitant use of rifampin.
8. History of non-compliance, inability to follow-up.
9. Pre-menopausal women (last menstruation ≤ 1 year prior to screening) who are not surgically sterile.
10. Ischemic stroke or hemorrhagic stroke within 90 days of LAA placement.
11. Anatomy unsuitable for LAA closure (incomplete surgical LAA ligation without suitable anatomy for Watchman placement. LAA ostial measurements >31mm, or <17mm in all views).
12. Requires long-term oral anticoagulation therapy for a condition other than atrial fibrillation.
13. ASA allergy, or confirmed allergy to nickel.
14. Prior PFO or ASD closure device or prosthetic or mechanical heart valve.
15. Acute MI within 90 days.
16. Platelets <50,000 at time of Watchman LAAC implantation.
17. Active endocarditis.
18. Planning for endocardial catheter AF or left atrial ablation within 90 days of Watchman implantation.

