### **Endpoints:**

Primary endpoint: Device associated thrombus (DAT) at 1-year follow-up imaging by either transesophageal echocardiogram or CT angiography depending on the patient tolerance for TEE (TEE preferred).

Secondary endpoints: Includes ischemic stroke, peripheral thrombo-embolic events, major bleeding requiring intervention (blood transfusion, or surgical or non-operative intervention, i.e., pericardial effusion, vascular access repair etc.).

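### Major bleeding is worded differently in the secondary endpoint and in the bleeding section, and a symptomatic critical-site bleed without transfusion or intervention falls outside the endpoint and is classed as minor

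*Combined protocol and SAP*

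**What the plan says.** All references are to the combined protocol and SAP.

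- **Endpoints** lists as a secondary endpoint "major bleeding requiring intervention (blood transfusion, or surgical or non-operative intervention, i.e., pericardial effusion, vascular access repair etc". It sets no unit threshold and no site restriction. The other components listed there are ischemic stroke and peripheral thrombo-embolic events.
- **Bleeding events** gives a two-way rule: "Bleeding will be classified as major or minor using the following guidelines". There are two routes to major. The first is "Bleeding associated with a transfusion of at least 2 units of blood or packed cells". The second is "Symptomatic bleeding in a critical area or organ requiring surgical or non-operative intervention", followed by seven sites: intraocular, intracranial, intraspinal, intramuscular with compartment syndrome, retroperitoneal, intra-articular and pericardial. The rest are residual: "Minor bleeds are clinical bleeds that do not fulfill the criteria for major bleeds". Stopping study drug is recorded as a feature of a minor bleed, so it does not make a bleed major.
- The same section states "Major bleeds will be further sub classified as either life-threatening or other major bleeds", and gives no criteria for the split.
- **Exclusion Criteria, item 6**, an eligibility rule, describes a major episode as a haemoglobin fall of at least 2 g/dL, or "transfusion of at least two units of blood, or symptomatic bleeding in a critical area" or organ, with no intervention condition. It goes on to "including life-threatening bleeding episode (symptomatic intracranial bleeding, bleeding with a decrease in the haemoglobin level of at least 5g/dL" and further criteria.
- **Background and Study Rationale**, in a sentence about availability of the reversal agent, gives a subdural or intracranial bleed as an example of a major bleed.

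Neither Endpoints nor Bleeding events refers to the other.

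**The concern.** Two questions arise. First, which wording decides whether a bleed counts towards the secondary endpoint? Second, does the intervention condition give a defensible label to a serious bleed that is only observed?

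Bleeding is central to the rationale. The objective in Study design includes keeping bleeding low by dropping clopidogrel, and the Background hopes for fewer major bleeds. The study may run at a primary center and up to 5 others. Central review is described for images, but none is described for bleeding, so consistency depends on the written definition. If that definition is ambiguous, two sites or two analysts can label the same event differently, and a symptomatic critical-site bleed can be tabulated among the minor ones.

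**Working it through.** The documents give no bleeding rate, hypothesis or power, so there is no plan figure to reproduce. The check applies each wording to the same cases.

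Endpoints can be read in two ways. On the *standalone* reading its own words define the event. On the *borrowed* reading, major takes its meaning from Bleeding events, and Endpoints only lists kinds of intervention.

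| Case | Endpoints, standalone | Endpoints, borrowed | Bleeding events |
|---|---|---|---|
| 1. Bleed with 2 or more units | in | in | major |
| 2. 1-unit transfusion, non-critical site | in | out | minor |
| 3. Access repair, under 2 units, non-critical site | in | out | minor |
| 4. Unlisted site (e.g. gastrointestinal), procedure, no transfusion | in | out | minor |
| 5. Symptomatic intracranial bleed, no transfusion, nothing counted as intervention | out | out | minor |
| 6. Symptomatic intracranial bleed, reversal agent only | in only if the agent counts | in only if the agent counts | major only if the agent counts |

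**Cases 2 to 4.** On the standalone reading these are endpoint events that Bleeding events calls minor. On the borrowed reading the two sections largely coincide. However, unqualified transfusion and the access-repair example then fit poorly, because neither by itself meets a route to major.

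**Case 5.** The event fails the 2-unit route and the intervention condition, so the residual rule makes it minor. It is outside Endpoints on both readings. The stroke component does not pick it up, since only ischemic stroke is listed. Under the exclusion 6 wording the same bleed would be major and life-threatening. The same gap applies to all seven listed sites.

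**Case 6.** The answer turns on the phrase non-operative intervention, which is not defined anywhere.

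**Scale of one relabelled event**, using exact (Clopper-Pearson) 95% intervals. For 0/n the upper limit is 1 − 0.025^(1/n). For 1/n the lower limit is 1 − 0.975^(1/n), and the upper limit solves (1−p)^n + n·p·(1−p)^(n−1) = 0.025.

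- Pilot, n = 100: shift 1/100 = 1.00 point. 0/100 gives 0 to 3.62%; 1/100 gives 0.03 to 5.45%.
- Optional expansion, n = 262: shift 1/262 = 0.38 point. 0/262 gives 0 to 1.40%; 1/262 gives 0.01 to 2.11%.

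These intervals hold for any single event. They show scale only and do not estimate how many bleeds are affected.

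**The case against.** The best defence is that one definition was intended. The phrase about surgical or non-operative intervention occurs in both Endpoints and Bleeding events, and both name a pericardial event. Endpoints also says major bleeding, so the standalone reading must give that adjective no meaning of its own before a 1-unit transfusion can enter. This makes the borrowed reading plausible. It does not explain the access-repair example or the missing threshold, and the text does not say which reading applies.

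It can also be said that both outcome sections carry an intervention condition, so it may be deliberate, and that the contrary wording sits in an eligibility rule and a drug-availability sentence. That is fair. Those texts do not override an outcome definition. They do show that the residual label departs from the protocol's own usage, so the condition needs a stated justification if it stays.

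The intracranial example is also narrower than it first looks. The reversal agent is to be available at every center, and if giving it counts as intervention, bleeds so treated are major. Availability is not use, however, and bleeds on aspirin alone after dabigatran stops remain.

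A reader might infer that both sections label the intracranial bleed minor. They do not: Endpoints has no minor category, and that label comes only from Bleeding events. A reader might also infer that such events are lost. The documents do not support that either, because adverse event recording, serious event reports, the 1-year AE review and the exit visit can all capture them. Capture is less assured later on. The adverse event definition runs to 90 days after implant, and routine serious event reporting to 30 days after dabigatran stops. Later bleeds therefore rest mainly on the 1-year review and exit visit.

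**Conclusion.** The point holds as a defect of definition. Two sections word major bleeding differently without saying which governs the endpoint. On the standalone reading they give different labels to the same bleed. On either reading, a symptomatic critical-site bleed with no transfusion and nothing counted as intervention is outside the endpoint and minor in Bleeding events. The life-threatening subclass cannot be applied consistently as written.

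The number of bleeds affected cannot be derived. It depends on what counts as intervention and on bleeding rates by type, which the documents do not give. A single relabelled event is small against sampling error at either sample size. The endpoint is descriptive, with no stated bleeding comparator, hypothesis or power. It would be wrong to read this as a demonstrated bias in favour of the regimen; nothing in the documents shows one. There is no effect on the sample size or power for device associated thrombus. The wording should be corrected because the outcome belongs to the stated objective and the correction is modest.

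**What to change.** 1. Reconcile Endpoints and Bleeding events into one outcome definition of major bleeding, and have the secondary endpoint cite it.
2. Define intervention, including whether giving the reversal agent counts.
3. Class symptomatic critical-site bleeds as major whether or not there was intervention, in line with exclusion 6. Otherwise, justify the condition and report untreated critical-site bleeds separately from minor bleeds.
4. Supply criteria for the life-threatening subclass and apply them only to bleeds already classed as major. Exclusion 6 can be drawn on. It includes a haemoglobin fall of at least 5 g/dL, and any haemoglobin element should apply only where values exist. Study design accepts PCV or hematocrit and leaves the morning-after check to hospital standard, and the Schedule of Study Procedures fixes no blood test between post-operative day 1 and day 90.
5. If the broader category in Endpoints is wanted, report it as a separately named outcome.

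**Cost.** These are changes to outcome wording and data capture only. If critical-site bleeds are classed as major regardless of intervention, the major-bleed rate will be equal to or higher than under Bleeding events as written; against Endpoints read alone it could move either way. The case report form needs fields for site, units transfused and intervention, because Recording of Adverse Events does not name them. The same fields are needed for bleeds after day 90, at the 1-year AE review and exit visit.

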## Serious Adverse Event Reporting to BI Pharmacovigilance

Adverse events classified by the treating investigator as serious require expeditious handling and reporting. Serious adverse events may occur at any time from informed consent until 30 days post cessation of dabigatran etexilate administration. BI must be notified of all SAEs containing at least one (1) fatal or immediately life-threatening event within five calendar days of the first knowledge of the event by the treating physician or research personnel. BI must be notified of all other SAEs within ten calendar days of the first knowledge of the event by the treating physician or research personnel. The SAE reports shall include all SAEs and non-serious AEs occurring in the same time and/or which are medically related and, in particular, the following information:

(i) the listedness of the reported events based on BI Investigator's Brochure for the dabigatran etexilate,

(ii) PI causal assessment as to whether the event(s) is/are related to the use of the dabigatran etexilate, and

(iii) the seriousness of each AE.

Causality should be assessed for each event as either "yes" or "no". No other variation should be reported. In case, according to the physician's causal assessment the association between an event and the patient's exposure to the dabigatran etexilate is classified as "unknown", the event will be considered "related" to the Study Drug for regulatory reporting purposes. If the SAE report forwarded to the BI was also submitted to a regulatory authority, this shall be indicated in the cover letter.

Supporting documentation for each of the reported SAEs, if requested by BI, will be provided to BI. Supporting documentation shall include, but is not limited to, lab reports, autopsy reports etc. SAEs, during and after pregnancy, will be reported to BI. To report an SAE, a BI SAE Reporting Form will be completed with the necessary information as available, and faxed using the following contact information:

Boehringer Ingelheim Pharmaceuticals, Inc. [name]  
[contact]**.

Follow-up information for SAEs and information on non-serious AEs that become serious will also be reported to BI as soon as it is available; these reports will be submitted using the BI SAE Reporting Form. Serious adverse events occurring more than 30 days after study drug administration need only be reported if a relationship to the dabigatran etexilate administration is suspected.

The investigator does not need to actively monitor participants for adverse events once the clinical trial has ended. However, if the investigator becomes aware of an SAE(s) that occurred after the participant has completed the clinical trial (including any protocol specified follow-up period), it should be reported to BI if the investigator considers it as relevant to the use of the BI study drug dabigatran.

**SAE Reporting to Regulatory Bodies:** Regardless of causality, all SAEs will be documented and reported to regulatory bodies, including the IRB as required by the International Conference on Harmonisation (ICH) Guidelines for Good Clinical Practice (GCP). Follow-up information for SAEs and information for non-serious AEs that become serious will also be reported in the same manner. SAE's will be reported to the Vanderbilt Human Research Protection Program according to their policies and procedures.

### **Study duration and timelines:**

From completion of the protocol, approval of contract and site initiation at Vanderbilt University Medical Center, study duration would be as follows: Estimated rate of enrollment is 2-3 subjects per site per month. Estimated time to complete enrollment of 100

subjects is 12 months once all sites are open, followed by 1 year of follow up to reach 1 year post implant imaging. Estimate completion of study in 24 months.

**Publications:**

Target Journals for publication of American College of Cardiology, Heart Rhythm, or Circulation Arrhythmia and Electrophysiology.

**Schedule of Study Procedures:**

	Baseline Visit	Procedure Day (+/- 3 days)	POD 1	90 Days Post Procedure (+/- 14 days)	1 Year Post Procedure (+/- 14 days)	AE/Other (e.g, DAT, study medication continued beyond 90 days)
Demographics	X					
H and P (including vital signs, height and weight)	X	X		X	X	X
I/E criteria (confirm eligibility)	X	X				
Informed Consent (a)	X	X				
CBC/BMP		X	X	X	X	X
Creat Cl	X	X	X	X	X	X
AE review	X	X	X	X	X	X
TEE		X (intra-operative)		X	X	X
Dispense Study Medication			X			X (as needed)
Pill Count/medication termination (planned)				X		X (as needed)
Exit					X	

(a) Informed Consent may be completed anytime up to one month prior to implant.

